11.6 STUDY RECORD RETENTION

All study documentation will be kept for a minimum of 3 years from the protocol defined end of study point. When the minimum retention period has elapsed, study documentation will not be destroyed without permission from the sponsor.

11.7 END OF STUDY

The end of study is defined as the last participant's last 6-month follow up. However, electronic health record follow up is planned thereafter.

The Investigators or the co-sponsor(s) have the right at any time to terminate the study for clinical or administrative reasons.

The end of the study will be reported to the REC, and R+D Office(s) and co-sponsors within 90 days, or 15 days if the study is terminated prematurely. The Investigators will inform participants of the premature study closure and ensure that the appropriate follow up is arranged for all participants involved. End of study notification will be reported to the co-sponsors via email to [contact]

A summary report of the study will be provided to the REC within 1 year of the end of the study.

11.8 CONTINUATION OF TREATMENT FOLLOWING THE END OF STUDY

CTCA is a diagnostic tool and not a treatment. Any treatment initiated during the study would be continued as recommended by the NICE or European Society of Cardiology Guidelines after the study conclusion.

11.9 INSURANCE AND INDEMNITY

The co-sponsors are responsible for ensuring proper provision has been made for insurance or indemnity to cover their liability and the liability of the Chief Investigator and staff.

The following arrangements are in place to fulfil the co-sponsors' responsibilities:

- The Protocol has been designed by the Chief Investigator and researchers employed by the University and collaborators. The University has insurance in place (which includes no-fault compensation) for negligent harm caused by poor protocol design by the Chief Investigator and researchers employed by the University.
- Sites participating in the study will be liable for clinical negligence and other negligent harm to individuals taking part in the study and covered by the duty of care owed to them by the sites concerned. The co-sponsors require individual sites participating in the study to arrange for their own insurance or indemnity in respect of these liabilities.

- Sites which are part of the United Kingdom's National Health Service will have the benefit of NHS Indemnity.
- Sites out with the United Kingdom will be responsible for arranging their own indemnity or insurance for their participation in the study, as well as for compliance with local law applicable to their participation in the study.

12 REPORTING, PUBLICATIONS AND NOTIFICATION OF RESULTS

12.1 AUTHORSHIP POLICY

Ownership of the data arising from this study resides with the study team. On completion of the study, the study data will be analysed and tabulated, and a clinical study report will be prepared. Any publications will be written in accordance with the ECTU Publication Policy.

12.2 PUBLICATION

The Clinical Study Report (CSR) will be submitted to the Sponsor and REC within 1 year of the end of the study. Where acceptable, a published journal article may be submitted as the CSR. The Chief Investigator will provide the CSR to ACCORD, for review, prior to finalisation. The clinical study report may be used for publication and presentation at scientific meetings. Investigators have the right to publish orally or in writing the results of the study.

12.3 DATA SHARING

Following publication of the primary paper, a de-identified individual participant data set will be submitted to a data archive for sharing purposes. Access to the de-identified dataset will be under a controlled access model in line with ECTU policies at that time.

12.4 PEER REVIEW

The study protocol has undergone independent review by an ECTU statistician and by the British Heart Foundation. The protocol has been developed in accordance with their recommendations.

14.1.1 Background

Many trials either fail to achieve their target numbers or require extensions and changes to recruitment strategies during trials to improve recruitment.¹ In the UK, a review of Medical Research Council and NIHR Health Technology Assessment Programme trials found that two thirds failed to reach their target recruitment despite more than half having extensions,² with follow-up studies finding no evidence of improvement over time.^{1,3} Failure to recruit is an international problem^{4,5} which has important negative consequences, including trials being underpowered, meaning that negative results are difficult to interpret, and abandonment of trials of potentially effective interventions.⁶ It also leads to considerable waste of resources. In one US academic centre over a four year period, 260 trials were abandoned after recruiting <2 patients costing the centre ~\$1 million in ethical review, set-up and contract negotiation.⁵

In response, all four UK countries have created infrastructure, like research networks, to improve trial recruitment, but there is also a need for research evaluate methods for optimising recruitment. The MRC START collaboration has published guidance on the design and reporting of such studies,⁷ which emphasises the importance of carrying out embedded randomised recruitment trials across a range of host trials to allow meta-analysis to maximise generalisability, explore heterogeneity, and to ensure adequate power.^{1,6} A recent Cochrane review of interventions to improve recruitment to trials identified relatively few such studies. Three strategies with some evidence of effectiveness were telephone reminders to initial non-responders, use of opt-out rather than opt-in procedures for contacting potential participants, and open designs where participants are not blinded to treatment allocation.⁸ The first two of these involve researchers directly contacting potential participants without their prior consent which is not standard practice in the UK, and the third is problematic from a risk of bias perspective.

This recruitment study is embedded in the SCOT-HEART 2 study. SCOT-HEART 2 is a two-parallel arm randomised trial examining two strategies for cardiovascular risk stratification to determine recommended cardiovascular primary prevention treatment: Computerised Tomography Coronary Angiography (CTCA) scanning to evaluate the presence of coronary artery disease vs usual care cardiovascular risk prediction tools based on measured characteristics like age, sex, blood pressure, smoking or cholesterol.

Recruitment from General Practitioner (GP) practices will be supported by the NHS Research Scotland (NRS) Primary Care research network (previously known as the Scottish Primary Care Research Network) using standard processes. The vast majority of patients invited will be identified in searches of GP records for potentially eligible patients, with the initial contact letter from the GP enclosing information about the study and inviting the patient to contact the research team if they

are interested (Appendix 1). The embedded Study Within a Trial (SWAT) will use a randomised controlled design to evaluate two interventions that may improve recruitment in this context of identification and initial contact in writing from the GP. Given that the chosen two interventions are of minimal cost, then even small increases in recruitment rates would be of value, and both interventions are straightforwardly applicable in other studies.

Intervention 1: short (intervention) vs full participant information sheet (PIS; standard practice control) enclosed with the initial GP contact letter

The study information included with the GP contact letter varies widely between studies in length and complexity. The full PIS is often excessive for the decision the patient is making (whether or not to contact the research team for more information) because it is designed to inform the decision to take part in the research (which comes after contacting the research team). There has been interest in whether providing more focused information at initial contact by the GP might lead to a higher recruitment rate, but there have been few trials investigating this.

The most recent Cochrane review identified two trials in this area,^{9,10} although one is only reported in abstract so information is limited.⁹ The fully reported study was embedded in the REACT trial evaluating computerised CBT in people with depression. 2479 patients were intended to be randomly sent either the full PIS (eight pages, conventional text-dominated comprehensive document aiming to inform the decision to participate) or a short PIS (two pages, leaflet format, including images aiming to inform the decision to initially contact the research team to discuss the study). 2230 were actually sent an embedded trial recruitment pack. In the short PIS arm, 134 (11.5%) responded and 63 (5.4%) were recruited. In the full PIS arm, 108 (9.3%) responded and 59 (5.1%) were recruited. In the context of a low overall recruitment rate, recruitment rates were higher in the short PIS arm (a 5.9% relative difference; absolute difference 0.3%, 95%CI -1.5 to 2.2) but not statistically significantly different. There was a statistically significant difference in the proportion of those initially contacted who were ineligible at screening (3.6% vs 2.2% of all patients responded and were ineligible, difference 1.4%, 95%CI 0.03 to 2.8). The authors concluded that a short PIS was ineffective, although their power calculation was based on an assumed response rate of 15% in the long PIS arm, and the observed relative difference of 5.9% exceeded their pre-specified effect size of 4.5%. The study was therefore underpowered, but did find evidence that a short PIS may decrease trial efficiency.¹⁰ The study reported only in abstract found differences in recruitment rate which were of similar magnitude but were not statistically significant.⁹ The Cochrane review concluded there was no evidence of benefit to recruitment, but that evidence quality was only moderate (that is “further research is likely to have an important impact on our confidence in the estimate of effect and may change the estimate”). The objective of this study is therefore to definitively evaluate the impact on recruitment of a short vs long (standard practice) PIS.

Intervention 2: contact letter envelope with an NHS logo printed on it (intervention) vs plain envelope (standard practice control)

There is no evaluation of this intervention in the trial literature that we are aware of, although there is literature in the related field of interventions to increase response to surveys, and some of these are potentially relevant to trial recruitment.¹¹ In the most recent Cochrane review, there was a single relatively small trial comparing envelopes with a study logo printed on them vs plain envelope which did not find a statistically significant difference.¹¹ However, there is a general belief that recruitment via the NHS (in this context, by the initial contact by the patient's GP) improves recruitment. It is therefore plausible that placing an NHS logo on the envelope increases the likelihood of the letter being opened and read. Although any intervention effect may be relatively small, the intervention is essentially zero-cost so even small effects would be worthwhile.

14.1.2 Aim and objectives

The aim of this embedded recruitment study is to examine the effect on recruitment of two interventions:

1. Short (intervention) vs full PIS (standard practice control) enclosed with the initial GP contact letter
2. Contact letter envelope with an NHS logo printed on it (intervention) vs plain envelope (standard practice control)

Objective 1: To examine the effect of each intervention compared to standard practice on rates of final trial recruitment

14.1.3 Methods

14.1.3.1 Public and patient participation

We have previously discussed recruitment studies of this type with the NRS Primary Care network West Node Public and Patient Participation group, and at a national meeting which included public and patient participants, members of NHS Research Ethics Committees and a representative from the Health Research Authority. There was agreement that improving recruitment is a legitimate concern, and that the decision to contact the research team was different to the decision to take part in the study (justifying the use of different participant information at each stage).

14.1.3.2 Trial design

This is a 2x2 factorial, parallel-group, 1:1:1:1 randomised trial.

14.1.3.3 Participants

All people sent an initial contact letter as part of SCOT-HEART 2 recruitment (broadly all adults aged 40-70 years with at least one risk factor for cardiovascular disease (Appendix 1; SCOT-

HEART 2 protocol for full details), who are not considered by the practice to be unsuitable to receive a letter.

14.1.3.4 Interventions

Intervention 1: Short (intervention) vs full PIS (standard practice control) enclosed with the initial GP contact letter

Intervention 2: Contact letter envelope with an NHS logo printed on it (intervention) vs plain envelope (standard practice control)

14.1.3.5 Outcomes

The primary outcome is:

- (1) The proportion of people sent a GP contact letter who are randomised into the SCOT-HEART 2 trial (overall recruitment rate).

14.1.3.6 Sample size

The Studies Within a Trial (SWAT) initiative¹² was established to develop protocols for embedded methodology studies that support pooling of data because sample sizes are defined by the host trial, not the embedded trial.^{6,7} Power calculations therefore do not determine study size, but inform estimates of how likely any single SWAT is to definitively evaluate the trialled recruitment intervention.

In this study, if 5% of those approached are randomised, and 5,000 remain to be randomised in SCOT-HEART 2 at the point where this study commences, then 100,000 could be approached and take part in this recruitment study. This would give us 90% power, with $p=0.025$, to detect a change from 5.0% to 5.5%.

If 10% of those approached are randomised, and 5,000 remain to be randomised in SCOT-HEART 2 at the point where this study commences, then 50,000 could be approached and take part in this recruitment study. This would give us 90% power, with $p=0.025$, to detect a change from 10.0% to 11.0%.

14.1.3.7 Randomisation

14.1.3.8 Randomisation will be stratified by GP practice and use permuted blocks.

14.1.3.9 Analysis

Statistical analysis will assume a null hypothesis of no difference in outcomes in the intervention and control arms. The primary analysis will compare the proportion of patients randomised, of those approached, by allocated intervention, separately for each intervention comparison. Results will be presented as risk ratios plus 95% confidence intervals, and corresponding p-value, from Poisson regression. The results will also be reported as an absolute difference. The primary analysis will assume that there is no interaction between the interventions, but a sensitivity analysis

will be performed to test this assumption (such as is possible, given the underpowered nature of interaction tests in this context). The primary analysis will be adjusted for GP practice and the effect of the other intervention comparison, but unadjusted analyses will also be presented. For each allocated intervention, separately for each comparison, the statistical report will provide the numbers of patients who are approached and the numbers randomised.

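### Does the embedded recruitment study need a restated significance level, given power at p=0.025 but 95% intervals for its two comparisons?

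*Protocol*

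**What the plan says.** The embedded study is a 2x2 factorial trial with equal allocation to four cells (Protocol, 14.1.3.2). It tests a short information sheet and an NHS-logo envelope. Its one primary outcome (14.1.3.5) is yes/no for each person: "The proportion of people sent a GP contact letter who are randomised into the SCOT-HEART 2 trial (overall recruitment rate").

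Section 14.1.3.6 gives two scenarios. If 5% of those approached are randomised, "then 100,000 could be approached and take part in this recruitment study", and "This would give us 90% power, with $p=0.025$, to detect a change from 5.0% to 5.5" per cent. If 10% are randomised, "then 50,000 could be approached and take part in this recruitment study", and "This would give us 90% power, with $p=0.025$, to detect a change from 10.0% to 11.0" per cent. The same section says that power does not set the study's size; the calculations "inform estimates of how likely any single SWAT is to definitively evaluate the trialled recruitment intervention".

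Section 14.1.3.9 says: "The primary analysis will compare the proportion of patients randomised, of those approached, by allocated intervention, separately for each intervention comparison". On reporting it says: "Results will be presented as risk ratios plus 95% confidence intervals, and corresponding p-value, from Poisson regression". It adds an absolute difference, adjustment for practice and for the other factor, unadjusted analyses, and the numbers approached and randomised by allocation. It gives no threshold and no multiplicity rule, and names no variance estimator for the Poisson model. The 5% level in section 8.1 belongs to the main trial.

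**The concern.** A reader who sees power at 0.025 expects the tests to be judged at 0.025. A reader who sees 95% intervals for two separate comparisons may judge each by whether its interval excludes 1, which is a 0.05 test. A comparison with p between 0.025 and 0.05 would then be positive to one reader and negative to the other. Because 14.1.3.6 uses power to say how likely the study is to be definitive, the level matters to that claim. Judging both comparisons at 0.05 would also allow a joint false-positive chance near 10%.

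A second, smaller worry is that Poisson regression applied to a yes/no outcome, with its ordinary model-based variance, overstates the standard error, and no robust variance is named.

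**Working it through.** **Inputs** (14.1.3.2 and 14.1.3.6). Each intervention is compared at its margin, half against half, so n = N/2 per side: 50,000 for 5.0% v 5.5%, and 25,000 for 10.0% v 11.0%. Stated power is 90% at p=0.025; the number of sides is not stated.

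**Reproducing the stated power.** For two proportions with mean p̄ and difference d,

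power = Φ{ [d − z·√(2p̄(1−p̄)/n)] / √([p1(1−p1)+p2(1−p2)]/n) }.

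Two-sided 0.025 gives z = 2.2414.
- 5.0% v 5.5%: (0.005 − 2.2414 × 0.0014106)/0.0014105 = 1.303, power 90.4%.
- 10.0% v 11.0%: (0.010 − 2.2414 × 0.0027419)/0.0027415 = 1.406, power 92.0% (91.8% with a continuity correction).

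The stated 90% is reproduced in the first scenario and is slightly conservative in the second.

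**Other readings.**

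| Reading | 5.0% v 5.5% | 10.0% v 11.0% |
|---|---|---|
| Two-sided 0.025, margins | 90.4% | 92.0% |
| Two-sided 0.05, or one-sided 0.025, margins | 94.3% | 95.4% |
| Two-sided 0.025, one cell v one cell | 60.5% | 63.2% |

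Only the first row fits. It equals 0.05/2 for two comparisons. That this was the reason for 0.025 is an inference; the protocol does not say so.

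**Where the two levels disagree.** A result is just significant when ln(RR) = z × SE, with SE² = (1−p1)/(n·p1) + (1−p2)/(n·p2) and the control rate held at 5% or 10%.
- 5%: RR = 1.0547 at z = 1.96 and 1.0627 at z = 2.2414.
- 10%: RR = 1.0532 and 1.0610.

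The mirror range is about 0.94 to 0.95. Under the planned effects, the share of trials landing in the band is the difference in power: 94.3 − 90.4 = 3.9% and 95.4 − 92.0 = 3.4%.

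**Joint false-positive chance**, treating the two margins as independent:
- 0.025 each: 1 − 0.975² = 4.94%.
- 0.05 each: 1 − 0.95² = 9.75%.

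**Poisson variance.** Under the null, the ratio of the model-based Poisson standard error to the binomial one is 1/√(1−p): 1/√0.95 = 1.026 and 1/√0.90 = 1.054. Under the alternatives it is 1.027 and 1.057. If model-based errors were used in a 0.025 test, the Poisson SE is √(1/2,500 + 1/2,750) = 0.02763 in both scenarios, and the true SEs are 0.02690 and 0.02615. With ln(1.1) = 0.09531:
- (0.09531 − 2.2414 × 0.02763)/0.02690 = 1.241, power 89.3%.
- (0.09531 − 2.2414 × 0.02763)/0.02615 = 1.276, power 89.9%.

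**The case for a change.** The best case for a change is that Appendix 1 has its own analysis section and names no separate analysis plan. It fixes 0.025 itself and then displays 95% intervals without saying which counts. The background in 14.1.1 aims at a definitive evaluation of the short information sheet, and that needs a level set before the data are seen. Section 14.1.3.10 also encourages other trial teams to follow this protocol, so an ambiguity could be copied. One sentence would remove it at no cost.

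Much of this is true. No level is stated in 14.1.3.9, and a sentence there would help. But it would record a policy, not correct an error. A 95% interval is a common format for estimation and pooling and can stand beside a test at 0.025, because the p-value is reported as well. Nothing in the section makes the interval the decision rule, so the natural reading is that 0.025 carries over. Keeping 0.05 per comparison would also be defensible for two distinct questions in a factorial trial. When either level would serve, the 9.75% is not a demonstrated harm of the plan as written.

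The variance point rests on silence: 14.1.3.9 does not say that model-based errors will be used. The choice of estimator belongs to an analysis plan.

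**Conclusion.** The observation is right, but no change follows. This is an unrepeated detail that analysts can fill sensibly: compare each reported p-value with 0.025 and keep the 95% intervals for estimation. On that reading the stated 90% power is met (90.4% and 92.0%) and the joint false-positive chance is 4.94%.

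The other reading affects a band of less than 0.01 in the observed risk ratio on each side of 1, and 3.4% to 3.9% of trials per comparison under the planned effects. The 9.75% figure depends on a decision rule the protocol does not state. Model-based Poisson errors, if used, would be 2.6% to 5.7% too large. That errs on the cautious side and leaves power at 89.3% and 89.9%.

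These results assume two-sided tests on the factorial margins, no interaction (as 14.1.3.9 assumes), and the recruitment rates and numbers in 14.1.3.6. The consequences stay within the embedded study. Its size is set by the host trial, and the counts it promises let others pool the results at whatever level they choose.

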14.1.3.10 Dissemination

As well as peer-reviewed publication of the findings, the study will contribute to future updates of the Cochrane systematic review of interventions to improve recruitment,¹ and other trial teams will be encouraged to follow this protocol through the Trial Forge initiative (see <http://www.trialforge.org> and this paper¹³) to ensure the availability of data for meta-analysis.

